Full study protocol and statistical analysis plan

Official Title of the study:

Umbilical cord and maternal blood concentrations of melatonin, soluble urokinase-type plasminogen activator receptor, and orosomucoid 2 in pregnancy complicated by preterm premature rupture of the membranes and histological chorioamnionitis

Date of the document:

October 2020.

Contents:

1. Participant Flow
2. Baseline Characteristics
3. Outcome Measures
4. Endpoints of the study
5. Limitations and Strengths
6. Certain Agreements
7. Results Point of Contact

1. Participant Flow

Recruitment Details

This observational case-control study will be conducted at the Department of Obstetrics and Gynecology, Cengiz Gokcek Public Hospital, Gaziantep, Turkey, between October 2020 and October 2021. The protocol was approved by the Ethics Committee for Clinical Research of Gaziantep University (reference no: 2020/276). The study strictly will be adhered to the principles of the Declaration of Helsinki. All subjects will be included in the study gave oral and written informed consent. 88 women were enrolled in the study in two groups.

Pre-assignment Details

The authors first will be assessed the recruited people to ensure meeting the inclusion and exclusion criteria. The inclusion criteria will be made according to the official documents.

Arm/Group Information *

There are two groups in the study.

Arm/Group Title *

preterm premature rupture of membranes group

Control group

2. Baseline Characteristics

To detect significant difference between groups according to lead levels with a moderate effect size (Cohen's $d=1$), minimum required sample size was estimated as 44 for each group ($\alpha=0.05$, $1-\beta=0.80$). Power analysis was performed by using G power package version 3.1. Kolmogorov Smirnov and Shapiro Wilk tests will be used to test the normal distribution of data. For comparing groups (PPROM/control) the student t-test will be used for variables that have a normal distribution, and the Mann Whitney U test will be used for variables that have not a normal distribution. The ROC analysis will be applied for the determination of cut-off point for variables. Moreover, Spearman correlation test will be used for the relationship of between variables. SPSS for Windows 22.0 and Medcalc programs will be used for statistical analysis. $p<0.05$ will be accepted as statistical significance.

3. Outcome Measures

Primary Outcome Measures: melatonin, soluble urokinase-type plasminogen activator receptor, and orosomucoid 2 concentrations

Secondary Outcome Measures: composite neonatal outcome (infant weight at delivery, neonatal intensive care unit hospitalization, and APGAR scores etc.)

Tertiary Outcome Measures: obstetric ultrasound examination and fetal-maternal assessment

4. Endpoints of the study:

The primary outcome in these analyses will compare maternal serum melatonin, soluble urokinase-type plasminogen activator receptor, and orosomucoid 2 measurements levels in study group and control group.

5. Limitations and strengths:

There will strengths of this study. The women participating in the study will recruit not received any treatment for PPRM at admission.

6. Certain Agreements

The authors declare that they have no conflict of interest.

7. Results Point of Contact

Corresponding Author: [name], Department of Obstetrics and Gynecology, Cengiz Gokcek Women's and Children's Hospital, Gaziantep, Turkey, [contact]

Address: [name]

GSM: [contact]

[contact]

[contact]

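### The sample-size sentence does not reproduce: Cohen's d = 1 at alpha 0.05 and 80% power needs 17 women per group, not 44, and the variable it names (lead) is not an outcome

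*Combined protocol and SAP*

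**What the plan says.** The only sample-size rationale is the opening sentence of section 2 (Baseline Characteristics). It begins "To detect significant difference between groups according to lead levels with a moderate effect size", gives that effect size as Cohen's d = 1, and concludes "minimum required sample size was estimated as 44 for each group" with alpha 0.05 and power 0.80. The software named is G*Power 3.1. Section 1 reports 88 women in two groups, which is exactly 2 × 44.

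For the group comparison, section 2 says "the student t-test will be used for variables that have a normal distribution, and the Mann Whitney U test" will be used for variables that are not normal. It sets significance at p < 0.05. It does not state whether the tests are one- or two-sided, and it gives no dropout allowance and no multiplicity adjustment.

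Section 3 lists "Primary Outcome Measures: melatonin, soluble urokinase-type plasminogen activator receptor, and orosomucoid 2 concentrations". Section 4 narrows this: "The primary outcome in these analyses will compare maternal serum melatonin, soluble urokinase-type plasminogen activator receptor, and orosomucoid 2 measurements levels" between the study and control groups. Lead is mentioned once, in the sample-size sentence, and nowhere else.

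**The concern.** Three things in one sentence do not fit together.

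- **The arithmetic.** A standardised difference of a full standard deviation is large. It needs far fewer than 44 per group for 80% power.
- **The label.** d = 1 is called moderate. By the usual convention moderate is d = 0.5, and that would need more than 44 per group. Neither reading gives the stated number.
- **The variable.** The calculation is for lead, while the plan's primary outcomes are three other analytes. As written, no primary analyte has a power statement.

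At stake is whether a reader can tell what the study was sized to detect. Taking d = 1 literally, the power is far above the stated 80%. Taking the word moderate literally, the reader would credit the study with 80% power at d = 0.5, which it does not have. Nothing elsewhere in the documents resolves this.

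**Working it through.** **Inputs, all from section 2:** d = 1; alpha 0.05; power 0.80; 44 per group, equal groups; Student t-test, or Mann-Whitney if not normal. Sidedness is not stated, so both options are shown.

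**Step 1. Try to reproduce 44.** The normal approximation per group is n = 2(z_alpha + z_beta)² / d².

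- Two-sided: 2 × (1.960 + 0.842)² / 1² = 15.7, so 16.
- One-sided: 2 × (1.645 + 0.842)² / 1² = 12.4, so 13.

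The exact noncentral-t calculation gives 16.71, so **17** per group two-sided, and 13.10, so **14** one-sided.

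**Step 2. Allow for choices the plan leaves open**, with d = 1 and, unless stated, two-sided testing at 80% power.

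| Variation | n per group |
|---|---|
| Mann-Whitney, efficiency 0.955 (normal data): 16.71 / 0.955 | 18 |
| Mann-Whitney, lower-bound efficiency 0.864: 16.71 / 0.864 | 20 |
| Bonferroni for three analytes (alpha 0.0167) | 23 |
| Bonferroni for six tests (three analytes, cord and maternal blood) | 27 |
| Power raised to 95%, alpha 0.05 | 27 |
| Power raised to 99%, alpha 0.05 | 38 |

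None of these gives 44. Dropout alone would have to be 1 − 17/44 = 61%. Reading 44 as the total (22 per group) gives 90% power, not 80%.

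**Step 3. Which d does 44 fit?** Exact two-sided t-test, 80% power:

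| d | n per group |
|---|---|
| 1.0 | 17 |
| 0.8 | 26 |
| 0.61 | 44 |
| 0.60 | 45 (normal approximation 2 × 7.849 / 0.36 = 43.6, so 44) |
| 0.5 | 64 |

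One-sided testing does not rescue the word moderate either: d = 0.5 then needs 51.

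**Step 4. What 44 per group delivers.** The noncentrality parameter is d × √(44/2) = 4.690 d.

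- d = 1: the normal approximation is Φ(4.690 − 1.960) = 99.7%; exact two-sided power is **99.6%**.
- d = 0.5: the normal approximation is Φ(2.345 − 1.960) = 65%; exact two-sided power is **64%**.
- Detectable d at 80% power: the normal approximation is 2.802 × √(2/44) = 0.597; exact is **0.604** two-sided (0.534 one-sided).
- With Mann-Whitney, two-sided: 0.604 / √0.955 = 0.62, and at the lower-bound efficiency 0.604 / √0.864 = 0.65.
- If alpha were 0.05 / 3 = 0.0167, two-sided t-test: 0.702.

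The stated number is 44 / 17 = 2.6 times what its own inputs require.

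**The case against.** The strongest reply is that the error lies on the safe side. At the stated d = 1, 44 per group has far more than the planned 80% power, and no passage commits the study to a smaller target. That is correct. A reader might infer that the study is underpowered; at its stated d it is not. Nor does the calculation argue for cutting the study to 17 per group, because 44 may be the intended figure and d = 1 the wrong entry. 44 fits d of about 0.6, but the documents cannot settle which entry is wrong.

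A reader might also infer that a null result could not be interpreted. That goes too far. A null result is read from the estimate and its confidence interval, and the sensitivity at 44 per group can be worked out from the sample size, alpha and test, as above.

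On lead, Cohen's d is standardised, so changing the noun does not change the arithmetic. This also stands. What the wrong noun leaves open is whether d was ever justified for melatonin, suPAR or orosomucoid 2. The text supports saying that lead is not named as an outcome; it does not support more than that.

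Finally, this is an observational study, and correcting the sentence alters no test or estimate. True, but it remains the plan's only sample-size rationale, and it cannot be reproduced by the method it names. Correcting the variable alone would leave the number wrong, and correcting d alone would leave the variable wrong.

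**Conclusion.** The sentence is wrong as written and should be corrected. Its inputs give 17 per group (two-sided t-test), 14 (one-sided) or about 18 to 20 (Mann-Whitney, two-sided), against a stated 44. It names a variable that is not an outcome, and it attaches to d = 1 a label that would conventionally mean d = 0.5 and 64 per group. The defect is in the justification, not in the adequacy of 44 per group for d = 1.

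The conclusion does not depend on sidedness, since the one-sided answer is further from 44. The figures of 99.6%, 64% and 0.60 assume a two-sided t-test at alpha 0.05, equal groups of 44 and no loss of data. The Mann-Whitney figures use the efficiency values shown. The 0.70 figure assumes a three-analyte Bonferroni correction. A reader might infer such a correction from the three primary analytes, but the plan states only p < 0.05.

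**What to change.** Keep 44 per group and rewrite the sentence.

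1. Recover the inputs entered in G*Power and establish whether d or the sample size was mis-stated.
2. Replace lead levels with maternal serum melatonin, suPAR and orosomucoid 2, as in section 4.
3. Delete the word moderate and state that the test is two-sided, if that is the intention.
4. Restate the figure in one of two ways:
   - *44 women per group give 80% power, at two-sided alpha 0.05, to detect a standardised difference of about 0.60 in each analyte by t-test (about 0.62 to 0.65 if Mann-Whitney is used).* If 0.60 was not the planning target, present it as the difference detectable at the chosen sample size, not as the reason for choosing it.
   - If d = 1 is the intended target, say why it is plausible for these analytes and give the power as 99.6% (two-sided t-test).
5. Add the detectable difference of about 0.70 at alpha 0.0167 only if the sponsor adopts a Bonferroni correction over the three analytes.

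The cost is one paragraph of wording and a check of the software output. No participants, measurements or analyses change.

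### The primary maternal serum comparison is unadjusted, and no matching or gestational-age window for controls is stated, so a gestational-age imbalance can produce a marker difference without any PPROM effect

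*Combined protocol and SAP*

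**What the plan says.** Section 1 (Recruitment Details) sets the design: "This observational case-control study will be conducted at the Department of Obstetrics and Gynecology". Under Arm/Group Information, "There are two groups in the study", a PPROM group and a control group. A control is not described further. Under Pre-assignment Details, "The inclusion criteria will be made according to the official documents", and those documents are not reproduced.

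Section 4 fixes the primary comparison on maternal blood: "The primary outcome in these analyses will compare maternal serum melatonin, soluble urokinase-type plasminogen activator receptor, and orosomucoid 2 measurements levels in study group" (the comparator being the control group). The title also names umbilical cord blood.

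The statistical methods are in section 2. The group comparison is: "For comparing groups (PPROM/control) the student t-test will be used for variables that have a normal distribution". When normality fails, the plan switches to a rank test: "the Mann Whitney U test will be used for variables that have not a normal distribution". The only other methods are ROC cut-offs and "Spearman correlation test will be used for the relationship of between variables". Neither adjusts the group comparison. No regression, stratification, matching or covariate list appears, and gestational age at sampling is not mentioned. Section 3 does list "Tertiary Outcome Measures: obstetric ultrasound examination and fetal-maternal assessment", so pregnancy assessment is part of the study, but the analysis makes no use of it.

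**The concern.** Nothing in an observational comparison balances the groups, so the control definition or the analysis has to. Here one group is preterm by definition and the other has no stated gestational window. A t-test or Mann-Whitney test takes no covariate. A marker that moves with gestation would therefore differ between groups sampled at different gestations, whatever its relation to membrane rupture. The same mechanism could also hide a real difference.

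This would be bias in the primary conclusion rather than imprecision. Recruiting more women would make a spurious result more likely to reach significance. Any ROC cut-off derived from the same data would inherit it.

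**Working it through.** **The plan's own figure.** Section 2 gives 44 per group for Cohen's d = 1, alpha 0.05 and power 0.80. This does not reproduce: an exact two-sided t-test needs 17 per group, and 44 per group has 99.6% power at d = 1. At 80% power, 44 per group corresponds to d of about 0.60 to 0.61. That is a separate matter. Only the group size of 44 is used below.

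**Inputs.** From the documents: n = 44 per group and a 0.05 significance level (taken as two-sided; the plan does not say). Assumed, because the documents give neither: r, the within-group correlation of the marker with gestational age, and D, the gap in mean gestational age in within-group SDs. The true PPROM effect is set to zero.

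**False-positive rate of the crude t-test.**

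- Apparent standardised difference: d = r × D.
- Noncentrality: d × √(n/2) = d × √22 = 4.690 × d, on 2 × 44 − 2 = 86 degrees of freedom.
- Example: r = 0.3 and D = 1 give d = 0.30, noncentrality 1.407 and rejection probability 28.5%.

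| r | D (SD) | apparent d | rejection rate |
|---|---|---|---|
| any | 0 | 0 | 5% |
| 0 | any | 0 | 5% |
| 0.2 | 0.5 | 0.10 | 7.5% |
| 0.3 | 0.5 | 0.15 | 10.7% |
| 0.2 | 1 | 0.20 | 15.3% |
| 0.3 | 1 | 0.30 | 28.5% |
| 0.2 | 2 | 0.40 | 45.8% |
| 0.3 | 2 | 0.60 | 79.5% |
| 0.4 | 2 | 0.80 | 96.0% |

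The rank test gives no protection. Simulated Mann-Whitney rejection (4,000 runs) is 25.6% at r = 0.3, D = 1 and 76.5% at r = 0.3, D = 2.

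**After adjustment.** With a linear relation, a model with group and gestational age holds the rate near 5%. Simulation (4,000 runs) gives 4.8% (D = 0.5, r = 0.3), 4.7% (D = 1, r = 0.3), 5.2% (D = 2, r = 0.3) and 5.2% (D = 1, r = 0.5).

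**Precision cost.** With equal groups, the variance of the group effect is inflated by 1 + D²/4: 1 + 1/4 = 1.25 at D = 1, and 1 + 4/4 = 2.0 at D = 2. The residual variance falls by the factor 1 − r² = 0.91 at r = 0.3. The noncentrality becomes 4.690 × d / √(0.91 × (1 + D²/4)), on 85 degrees of freedom:

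- True d = 1: 4.398 at D = 1 and 3.477 at D = 2, giving power of about 99% and 93%.
- True d = 0.6: 2.639 at D = 1 and 2.086 at D = 2, giving power of about 74% and 54%.

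**The case against.** The strongest reply is that the documents do not show an imbalance. Maternal blood can be drawn from undelivered controls at the same gestation as the PPROM women, and the eligibility documents, which are not available here, may require that. This stands. The supportable statement is that no matching is stated, not that there is none. If matching on gestational age at sampling was used, most of the problem for maternal serum disappears and the plan need only say so.

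A reader might infer that gestational age must differ, because cord blood is taken at delivery. That argument bears on cord samples, where a difference is likely unless controls also deliver preterm. Section 4 makes maternal serum the primary comparison, so the argument does not carry over. Even for cord blood, part of a gestational-age difference may follow from PPROM itself, and the plan does not say whether that part should be removed.

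A reader might also take the upper rates as the expected error. The documents support no particular r or D, and mild values give rates only slightly above 5%. Nor is d = 0.60 an effect that the study set out to detect. It is back-calculated from 44 per group; the only stated effect is d = 1. Reaching that spuriously needs, for example, r = 0.5 with a 2-SD gap.

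Finally, if the groups barely overlap in gestational age, regression extrapolates and cannot rescue the comparison. This also stands, for maternal and cord samples alike, and the fix allows for it.

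**Conclusion.** The concern holds in conditional form. As written, the primary comparison has no protection against a gestational-age difference, either in the stated design or in the analysis, and such a difference can by itself produce a significant result. Under the assumed values the false-positive rate at 44 per group runs from 5% to 96%, so the true size cannot be known from the documents. The figures assume a linear relation, equal within-group variances, two-sided 0.05 and no true PPROM effect. That the primary result is biased, or that the groups do differ in gestational age, is not established. For cord blood an imbalance is likely, but that comparison is not primary.

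**What to change.** - **Primary analysis.** For each maternal serum marker, fit a linear model on log concentration with group and gestational age at sampling. Report the adjusted geometric-mean ratio with its 95% confidence interval. Keep the t-test or Mann-Whitney result as a crude sensitivity analysis.
- **Further covariates.** Maternal age and clock time of the draw may be added if recorded. Clock time would be a new item, since nothing in the documents says that it is collected.
- **Overlap.** For maternal and cord samples alike, make adjusted comparisons only over the gestational ages that the groups share. Where there is no overlap, report levels descriptively and make no PPROM claim.
- **Controls.** Define the control group and its gestational window in the plan, and state any matching already used. If controls are still being recruited, frequency-match on gestational week at the maternal draw. Section 1 is mostly in the future tense but reports 88 women as already enrolled, so matching may no longer be possible; adjustment still would be.

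The cost is a change of SAP wording and recording gestational age at each sample. The downside is the loss of precision shown above, which is material at a 2-SD gap for effects near d = 0.6 (power about 54%) and small for d = 1 (about 93%). Restriction to overlapping gestations would also reduce the number of women analysed.

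### ROC cut-offs will be derived from the 88 study women with no validation or optimism correction planned, so accuracy reported at them would be modestly overstated

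*Combined protocol and SAP*

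**What the plan says.** The whole ROC plan is one sentence in section 2 (Baseline Characteristics), which also holds the statistical methods: "The ROC analysis will be applied for the determination of cut-off point for variables". It gives no rule for choosing the point on the curve, no threshold set beforehand, no expected direction for each marker, no interval estimate, and no split sample, cross-validation or bootstrap. On software it says only "SPSS for Windows 22.0 and Medcalc programs will be used for statistical analysis".

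The only data described are those of this study. Section 1 states "88 women were enrolled in the study in two groups", and section 2 states "minimum required sample size was estimated as 44 for each group".

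The ROC step is not the primary analysis. Section 3 lists "Primary Outcome Measures: melatonin, soluble urokinase-type plasminogen activator receptor, and orosomucoid 2 concentrations", and section 4 defines the endpoint as a comparison between groups: "The primary outcome in these analyses will compare maternal serum melatonin, soluble urokinase-type plasminogen activator receptor, and orosomucoid 2 measurements levels". That comparison uses the t test or the Mann-Whitney test on continuous levels.

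**The concern.** A cut-off picked from an empirical ROC curve is the point that separated this particular sample best. It follows chance features of the sample as well as any real difference between the groups. When sensitivity and specificity are then read off the same curve, the chance part counts as accuracy, and it would not recur in new women. Standard ROC output does not remove this bias. With 44 women per group the chance part is large enough to matter.

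What is at stake is the numerical accuracy attached to each cut-off. A reader could apply a published cut-off directly, and would expect the published sensitivity and specificity to hold.

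**Working it through.** **1. The plan's own figure.** The stated sample size uses a standardised difference d = 1, α = 0.05 and power 0.80. The normal formula for a two-sided test gives n = 2(1.960 + 0.842)² / 1² = 15.7, so 16 per group (17 by the t test). The stated 44 does not reproduce from these inputs. That is a separate matter. Here 44 is used simply as the group size available for the ROC curves. With 44 per group, the same formula gives 80% power at d = √(15.70/44) = 0.60, so d = 0.6 and d = 1 are both natural values to examine.

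**2. Inputs.** From the documents: 44 versus 44, and d = 1. Assumed: the cut-off maximises J; markers are normal with equal variance in the two groups; d = 0, 0.5 and 0.6 are added to show the range. Direction means whether high or low values indicate a case. It is either fixed beforehand or chosen from the data.

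**3. A marker with no value: exact result.** If the marker carries no information, every ordering of the 88 women is equally likely, so no normality assumption is needed. With direction fixed, the largest apparent J is at least k/44 with probability C(88, 44+k) / C(88, 44). Summing over k = 1 to 44:

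mean J = (1/44) × ½ × [2⁸⁸ / C(88, 44) − 1] = (1/44) × ½ × (11.791 − 1) = 5.395/44 = 0.123.

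The true J is 0. If the direction is also taken from the data, the corresponding two-sided sum gives 0.174.

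**4. Markers with a real difference: simulation.** There were 10,000 simulated data sets per row. Apparent values come from the 88 women who supplied the cut-off. True values are for the same cut-off in new subjects.

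| d | Direction | Apparent Se / Sp | True Se / Sp | Apparent J | True J | Excess J |
|---|---|---|---|---|---|---|
| 0 | fixed | 0.543 / 0.579 | 0.483 / 0.517 | 0.122 | 0.000 | 0.122 |
| 0 | from data | 0.586 / 0.587 | 0.499 / 0.501 | 0.173 | 0.000 | 0.173 |
| 0.5 | fixed | 0.631 / 0.651 | 0.578 / 0.599 | 0.282 | 0.177 | 0.105 |
| 0.6 | from data | 0.651 / 0.669 | 0.598 / 0.616 | 0.320 | 0.214 | 0.106 |
| 1 | fixed | 0.714 / 0.738 | 0.668 / 0.693 | 0.452 | 0.361 | 0.091 |

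The d = 0 rows agree with step 3. At d = 0.6 the excess is 0.651 − 0.598 = 0.053 in sensitivity and 0.669 − 0.616 = 0.053 in specificity. At d = 1 it is 0.714 − 0.668 = 0.046 and 0.738 − 0.693 = 0.045. As a share of apparent J, this is 0.106/0.320 = 33% and 0.091/0.452 = 20%.

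**5. Comparison with the best attainable.** Even the ideal cut-off has J = 2Φ(d/2) − 1, which is 0.236 at d = 0.6 and 0.383 at d = 1. The mean apparent values (0.320 and 0.452) exceed what any cut-off on such a marker could deliver.

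**6. The AUC.** Choosing a cut-off does not inflate it. The mean empirical AUC was 0.759 against a true 0.760 at d = 1, and 0.499 against 0.500 at d = 0 with direction fixed. It rises to 0.549 at d = 0 if the direction is chosen from the data, which is why direction should be fixed too.

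**The case against.** The strongest reply is that the plan never says it will report sensitivity or specificity, never names Youden's J, and never says the cut-off will go unvalidated. All three are read from a single sentence and from silence. This is fair, and the conclusion is conditional on them. But a cut-off has little use without its sensitivity and specificity, and no second data set or resampling step is described. Following the plan as written therefore gives uncorrected figures.

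A second reply is that the effect is modest and lies outside the primary analysis. Both parts stand. J adds two errors together; on each of sensitivity and specificity the excess is about 5 points for a real marker. The t and Mann-Whitney comparisons use continuous levels and do not depend on any cut-off.

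A reader might infer that a useless marker will appear to discriminate. The figures do not support so strong a statement. With direction chosen from the data, such a marker typically shows about 59% sensitivity and 59% specificity. By the formula in step 3, its apparent J reaches 0.30 (k = 14) in about 1% of data sets with direction fixed, and about 2% otherwise. A two-sided test of its AUC is significant in only about 5% of data sets.

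A reader might also infer inflated error rates from significance tests on the dichotomised marker, misleading predictive values from the equal-sized groups, or larger bias within a chorioamnionitis subgroup. The documents plan no test at a cut-off, no predictive values and no subgroup ROC analysis, and give no chorioamnionitis count. None of these can be charged against the plan.

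**Conclusion.** The concern holds in a limited form. Accuracy reported at cut-offs derived from these 88 women, without correction, would be optimistic on average:

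- about 5 percentage points each on sensitivity and specificity for a marker with d between 0.5 and 1;
- about 6 points each for a marker of no value with direction fixed, and about 9 with direction chosen from the data.

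The result for a marker of no value is exact for 44 versus 44, given the Youden criterion and no ties. The others also assume normal, equal-variance markers, and another criterion or distribution would change the sizes. That sensitivity and specificity will be reported is an inference from the plan, though a natural one. The issue concerns a supplementary analysis. It should be corrected, but it does not threaten the primary comparison.

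**What to change.** Replace the single ROC sentence with a short specification:

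- State the expected direction of each marker and the criterion for choosing a cut-off before the data are examined.
- Make the AUC with its 95% CI the main ROC result for each marker.
- For any cut-off reported, give optimism-corrected sensitivity and specificity. Repeat the cut-off selection inside every bootstrap resample; cross-validation that repeats the selection in each fold is an acceptable alternative.
- Label the cut-offs as exploratory until they are validated in other women.

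No additional participants or measurements are needed. The cost is a short script and slightly less favourable accuracy figures.

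### Three primary maternal-serum comparisons are each tested at an unadjusted 0.05, so the chance of at least one false-positive primary result can reach about 14% instead of 5%

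*Combined protocol and SAP*

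**What the plan says.** Section 3 (Outcome Measures) gives three analytes equal primary status: "Primary Outcome Measures: melatonin, soluble urokinase-type plasminogen activator receptor, and orosomucoid 2 concentrations". It names no specimen. Section 4 (Endpoints of the study) supplies it: "The primary outcome in these analyses will compare maternal serum melatonin, soluble urokinase-type plasminogen activator receptor, and orosomucoid 2 measurements levels" in the study and control groups. Read together, the two sections give three primary comparisons, all in maternal serum.

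The statistical methods are in section 2 (Baseline Characteristics). The test is chosen variable by variable: "the student t-test will be used for variables that have a normal distribution, and the Mann Whitney U test will be used" for the others. The single decision rule is that p<0.05 "will be accepted as statistical significance". The sample-size statement uses one comparison with Cohen's d=1, alpha 0.05 and power 0.80, and says that the "minimum required sample size was estimated as 44 for each group". It is written for lead levels, which are none of the three markers, so it does not show which marker the study is built around.

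The official title also covers a second specimen: "Umbilical cord and maternal blood concentrations of melatonin, soluble urokinase-type plasminogen activator receptor, and orosomucoid 2". Cord blood appears in no outcome list and in no analysis statement.

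The document contains no multiplicity adjustment, testing order or lead marker. It has no rule that all three markers must be significant, and no statement that the comparisons are exploratory.

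**The concern.** With three primary outcomes and no rule for combining them, the plan does not say what a positive primary result is. As written, a difference in any one marker at p<0.05 could be reported as a positive primary finding. The 5% error rate then applies to each test separately and not to the primary question as a whole. A lead marker chosen after the results are known could not repair this, because the choice could follow the smallest p-value. What is at stake is how much weight a single significant marker out of three can carry.

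**Working it through.** **Inputs.** Number of primary tests: 3 (sections 3 and 4). Threshold per test: 0.05, unadjusted (section 2). Size: 44 per group (section 2). Effect size: d=1 (section 2). The plan does not state sidedness; two-sided tests are assumed. It gives no correlations between the markers, so a range is shown.

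**The plan's own figure.** The plan states no family-wise error rate to reproduce. It does state 44 per group for d=1, alpha 0.05 and power 0.80. The normal approximation gives n = 2 × (1.960 + 0.842)² / 1² = 15.7, so 16 per group; the exact t-test calculation gives 17. The stated 44 is not reproduced. It corresponds to d of about 0.6, since 2 × (1.960 + 0.842)² / 0.6² = 43.6, so 44 (45 by the t-test). That mismatch is a separate matter. It is relevant here because d=1 and d=0.6 give very different answers on what adjustment costs.

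**Family-wise error as planned, all three nulls true.** For independent tests it is 1 − (1 − 0.05)³ = 1 − 0.857 = 0.143. For correlated tests, equicorrelated normal test statistics were simulated (1,000,000 draws, two-sided critical value 1.96):

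| Assumed correlation | Chance of at least one p<0.05 |
|---|---|
| 0 | 14.3% |
| 0.3 | 13.6% |
| 0.5 | 12.5% |
| 0.7 | 10.9% |
| 0.9 | 8.4% |

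Every value exceeds 5%.

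**Family-wise error with Holm.** The ordered p-values are compared with 0.05/3 = 0.0167, then 0.05/2 = 0.025, then 0.05. When all nulls are true, a false positive requires the smallest p-value to pass the first step. Under independence the error is therefore 1 − (1 − 0.0167)³ = 4.9%. Holm keeps it at or below 5% under any correlation.

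**Cost in power.** Noncentral t with 44 per group, df = 86 and noncentrality d × √(44/2). The second column is the power for one marker if it has to pass at Holm's first step:

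| | alpha 0.05 | alpha 0.0167 |
|---|---|---|
| Power at d=1 (plan) | 99.6% | 98.7% |
| Power at d=0.6 (assumed) | 79.5% | 64.6% |
| d detectable with 80% power | 0.60 | 0.70 |

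The plan allows Mann-Whitney, so 0.70 is not a ceiling. Scaling 44 by the test's efficiency under normality gives 44 × 0.955 = 42.0 and a detectable d of about 0.72. The worst-case efficiency gives 44 × 0.864 = 38.0 and about 0.76.

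**The case against.** The strongest counter-argument is that inflation depends on a decision rule that the plan never states. If success required all three markers to be significant, there would be no type I inflation. If each marker is its own hypothesis and is reported as such, the error for each stays at 5%. Whether to adjust across distinct biomarkers in an observational case-control study is partly a matter of judgement, and the document ties no treatment or stopping decision to the result. Part of this stands: it argues against treating the gap as fatal. It does not remove the gap. No all-must-succeed rule is written, the study is not labelled exploratory, and the plan names primary outcomes, a significance level and a target power.

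A second objection is that 14% is a ceiling, not an estimate. That is correct. It needs independent tests and three true nulls. The markers are measured in the same women, so positive correlation is plausible and the figure would then be lower.

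A third is that the cost of adjustment looks negligible only at d=1, an effect size that does not reproduce the stated sample size. That also stands, and it is why the loss at d=0.6 is shown.

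A reader might infer from the title that there are six primary comparisons (three markers in two specimens), giving 1 − 0.95⁶ = 26.5% under independence. The documents do not support that as the primary error rate. Section 4 restricts the primary comparison to maternal serum, and cord blood appears only in the title.

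**Conclusion.** The point holds for the three maternal-serum comparisons. Followed as written, with any single marker below 0.05 open to being reported as a positive primary result, the plan allows a family-wise error of up to about 14% when all three nulls are true. Across assumed correlations from 0 to 0.9 the range is 14.3% to 8.4%, always above 5%. This rests on two-sided tests, a common correlation between test statistics, and the absence of any stated rule joining the three results. It is a should-fix: the gap concerns the main claim and is cheap to close, but reporting all three results openly would already limit the harm. It does not follow that a significant marker would be a false finding, or that the secondary outcomes need to change status.

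**What to change.** Add to the statistical methods in section 2, and cross-refer from section 4: the three maternal-serum comparisons (melatonin, suPAR, orosomucoid 2) form the primary family and are tested with Holm's procedure at an overall two-sided 0.05; all three results are reported with unadjusted and Holm-adjusted p-values; any cord-blood comparison is outside the primary family. The neonatal outcomes stay secondary, as prespecified.

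The change needs no extra participants, samples or assays. The cost is that the smallest of the three p-values must fall below 0.0167 before anything can be declared significant. At d=1 that costs about one percentage point of power per marker (99.6% − 98.7% = 0.9). At an assumed d=0.6 it costs about 15 points at the first step (79.5% − 64.6% = 14.9); Holm's later steps are less strict, so this is the most that a marker can lose. If the sponsor finds that too high, naming one marker as the single primary outcome before any results are seen would keep its test at 0.05, with the other two moved to secondary.
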